9.2.5. Visit 4: YSI FST

For those subjects randomized to Day 1 who have not already received study training and iPro2 placement and sensor insertion from Visit 3, all the procedures previously listed at Visit 3 will be completed at this visit. Investigational center staff will follow:

- Overview general study procedures (Section 9.2.4.1)
- Overview study devices and supplies (Section 9.2.4.2)
- Overview training and (Section 9.2.4.3)

Subjects will undergo one YSI FST on any one of the following sensor wear days:

- Day 1 (1 – 25 hours)
- Day 3 – 4 (49 – 97 hours)
- Day 6 (121 – 145 hours)

The YSI FST is a 7 hour frequent BG sampling session using IV blood samples and a laboratory BG analyzer, YSI. The investigational center staff will set up the YSI.

9.2.5.1. Prior to Arrival at the Clinic for the YSI FST

- On the evening prior to FST, subjects will be asked to fast for approximately 12 hours and adjust their insulin and medications according to routine care (for example as they would do for fasting lipid panel). Subjects may fast for shorter period of time **based on investigator discretion.**
- **The feeding protocol may be modified based on investigator discretion.**

9.2.5.2. In-Clinic Procedures

Overview general study procedures

Investigational center staff will:

- Perform applicable calibrations on the YSI instruments
- Synchronize study laptop computer and YSI devices at the investigational center synchronized with the designated study clock
- Refer to Table 2 for instructions on YSI FST Timing and fingerstick requirements.
- Conduct YSI FST procedures
- Provide YSI data to sponsor
- Instruct subjects on returning to clinic for early dislodgement of Enlite Sensors (Section 9.6)
- Remind subjects to perform fingersticks (capillary SMBG)
- Remind subjects to bring in the Study Meter at next visit date
- Remind subjects to contact investigational center staff for technical issues and support
- Review the next visit date and time
- Enter eCRFs into the study database as appropriate
- Address questions or concerns from subjects
- Assess subjects for the occurrence of any adverse events or device deficiencies (see Section 11 and Section 13) at each visit and document on the appropriate source; record event(s) on the appropriate eCRF
-

9.2.6. Visit 5: End of Study

- Subjects will return to the clinic to remove their study devices
- Investigational Center staff will review documentation of time they calculated for T=145 hours where the sensor may be removed at that time or after that time to ensure that the devices are not removed pre-maturely
- Investigational center staff will address questions or concerns from subjects
- Investigational center staff will ask subjects about the occurrence of any AEs or device deficiencies.
- Investigational center staff will:

- Download the iPro2 data from CareLink iPro following completion of the study devices wear
- Obtain subject's Study Meter BG values and enter into CareLink iPro
- Collect subject's Patient Log Sheet
- Provide iPro2 data to sponsor
- Investigational center staff will perform a Skin assessment on the area of each of the Enlite Sensor insertion sites and document in subject source and complete the Skin Assessment eCRFs
- Investigational center staff will collect returned devices (See Table 1 in Device Accountability section) and unused supplies from subjects
- Subjects will complete a questionnaire about their Enlite Sensor experience.
- Primary sensor and secondary sensor will be randomly assigned via RDC.
- An Exit eCRF will be completed at this visit.

9.3. Subject Consent

ICF will be obtained in accordance with the CFDA Order No. 25. Prior to entry into the study, The Ethics Committee (EC)- and Medtronic-approved ICF will be given to each subject or their legally authorized representative or guardian (if applicable) to complete. Subjects or their legally authorized representative or guardian will be offered the opportunity to review these documents away from the investigational center.

The investigator or designee will explain the purpose and duration of the study, requirements of the subject during the study, as well as the potential risks involved with participation in this study. Every attempt will be made to answer subject's or their legally authorized representative or guardian questions during the informed consent process. The process for obtaining informed consent shall not waive or appear to waive subject's legal rights. The consenting process shall use language that is non-technical and understandable to the subject or legal representative. The consenting process will be documented. It will include a dated signature of the subject or legal representative acknowledging their participation in the study is voluntary. In addition, it will include a dated signature of the principal investigator or an authorized designee responsible for conducting the informed consent process. The subject or their legally authorized representative or guardian will receive copies of the fully executed documents. A subject's participation in study procedures cannot start before the consent process has been properly executed.

If the ICF is amended during the course of the study, the EC shall determine if active subjects must be re-consented at their next visit and whether subjects who have completed the study at the time of the amendment do not need to repeat the informed consent process.

Subjects will be informed that competent authorities from the investigational center, Medtronic, and specific agencies, such as the CFDA and the EC, may have access to the clinic records that reveal their identity and health care information.

The investigational center must report the following informed consent violations to the sponsor:

- Failure to obtain informed consent from subject.
- Failure to obtain informed consent prior to performing one or more study procedures.
- Failure to maintain ICFs on file for all subjects who have provided informed consent.
- Use of an ICF that has not received approval from the EC.
- Use of an incorrect version of the ICF.

9.4. Randomization and Treatment Assignment

Investigational Centers will receive this randomization assignment generated electronically in the study database from Medtronic. The first randomization scheme assigns the subjects to one of the following sensor wear days (Day 1, 3-4, or 6) which determines when they will be participating in the in-clinic YSI FST.

Once subject is assigned to the study group, subjects will stay in that randomization group during the study.

In addition, at the end of the study (Visit 5), another randomization scheme will be done to assign the primary and secondary sensor for each subject.

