9.6. Replacement Sensors

If subjects have either of the sensors which has dislodged any time prior to YSI FST visit or within a duration of 5 hours YSI FST, subject will be asked to re-insert both sensors. And re-insertion of Enlite Sensors will be done only once.

Any YSI FST with a duration of 5 hours or more before sensor dislodgement will be considered complete and will not need to be rescheduled.

Subjects will be issued replacement Enlite sensors to be inserted at Clinic but at the date and time specified by the Clinic.

Subject will wear the replaced sensors for 6 days and attempt to complete the required YSI FST visit.

Subjects will have their YSI FST visit rescheduled per the original randomized FST Group.

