Upon exiting from the study, no further study data will be collected or study visits will occur for the subject. All data available through the time of the subject's exit will be used for analysis. In the event of study exit, the investigator should discuss with the subject the plans for future care and treatment. The investigator should explain that the subject will continue to receive standard medical care. Alternative treatment, such as medication options or follow-up through standard of care procedures instead of study procedures, and medical consequences should also be discussed. Source documentation of this conversation recommended. The investigator must notify the subject of any significant new findings that may become available during the course of the study, which are pertinent to the safety and well-being of the subject.

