14.6. Analysis Populations, handling of missing data, error

Data entry error or non-reasonable values will be cleaned before data analysis. No imputations will be done for missing data. All enrolled subjects who have at least one paired Enlite Sensor and YSI measurement will be included in the efficacy analysis population. All enrolled subjects who have a Enlite Sensor inserted will be included in the safety analysis population.

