16.13.2. Subject follow-up in case of termination

In case of early investigational center suspension or termination, all subjects should be contacted to plan an early Termination visit at the Investigational Center. All efforts will be made to complete and report all study observations at the time of termination. The subject will return the study devices to the investigational center (unless subject is allowed to keep them per country requirement), receive appropriate treatment and follow-up.

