6.3 Analysis Population

Full analysis set (FAS^{#1}): a set of subjects who have a Enlite Sensor inserted.

Full analysis set (FAS^{#2}): a set of subjects who have a Enlite Sensor inserted and have at least one paired Enlite Sensor and YSI measurement.

Per-Protocol Set (PPS) refer to the subgroup population of FAS^{#2} who have no major protocol violations (subjects that violate the inclusion criteria, meet the exclusion criteria, etc.).

Safety Set (SS) will use the same definition method of FAS^{#1}, hence it will not be defined alone in the analysis.

Primary efficacy analysis and secondary efficacy analysis will be analyzed based on both the FAS^{#2} and PPS. All the baseline demographic data and safety evaluation will be analyzed based on the FAS^{#1}.

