6.6 General Considerations for Data Analysis

6.6.1 Data Collection

(1) Primary endpoint, secondary endpoints, and other descriptive endpoints will be based on retrospective data collected from primary sensor.

(2) Precision analysis will be based on data collected from both sensors.

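### Is the primary analysis left undefined for a subject with sensor-YSI pairs who leaves before the primary sensor is drawn, or whose drawn sensor has no pairs?

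*Protocol*

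**What the plan says.** **The draw.** Protocol 9.4 places it at the last visit: "at the end of the study (Visit 5), another randomization scheme will be done to assign the primary and secondary sensor for each subject". The Visit 5 task list in Protocol 9.2.6 repeats this: "Primary sensor and secondary sensor will be randomly assigned via RDC". The timelines in the Protocol synopsis, Protocol 9.1 and SAP 5.5 put it there too. The recorder download and the entry of meter values into CareLink iPro are also Visit 5 tasks.

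**The endpoint.** SAP 6.6.1 says that the primary, secondary and other descriptive endpoints "will be based on retrospective data collected from primary sensor". Protocol 14.8.1 agrees. SAP 7.6 puts the t-test at subject level.

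**The analysis set.** Protocol 14.6: "All enrolled subjects who have at least one paired Enlite Sensor and YSI measurement will be included in the efficacy analysis population". SAP 6.3 defines FAS#2 as "a set of subjects who have a Enlite Sensor inserted and have at least one paired Enlite Sensor and YSI measurement" and runs the primary analysis on FAS#2 and the per-protocol set. Neither definition says that the pair must come from the primary sensor.

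**Withdrawal and missing data.** Protocol 9.13: "All data available through the time of the subject's exit will be used for analysis". It also rules out study visits after exit and requires the devices to be returned. SAP 6.5 includes withdrawn subjects in the final analysis and bars imputation of missing primary data. Protocol 14.9 bars it for the primary endpoint as well.

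**Replacement.** Under Protocol 9.6, dislodgement before the FST or within its first 5 hours leads to new insertion of both sensors, with one limit: "And re-insertion of Enlite Sensors will be done only once".

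**Early termination visit.** The only one described is in Protocol 16.13.2, for suspension or termination of a centre: "all subjects should be contacted to plan an early Termination visit at the Investigational Center".

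**The concern.** Membership of the efficacy set depends on either sensor, while the value to be analysed depends on one sensor chosen later at random. The two can come apart in two ways.

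- **Route (a):** the subject completes the FST on Day 1 or Day 3-4 and leaves before Visit 5, so no primary sensor is ever drawn.
- **Route (b):** the draw is made, but the chosen sensor has no YSI pairs while the other has some. The replacement rule covers dislodgement, and only once. It does not cover a second dislodgement or a sensor that stays in place without valid readings.

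The primary test is the study's only pass/fail criterion. If the plan does not fix who enters it and with which sensor, the number tested can differ from the declared FAS#2. The choice between omitting the subject, making a late draw and using the other sensor could then be made after both sensors' data have reached the sponsor.

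**Working it through.** **1. The plan's sample size.** Inputs from Protocol 14.5 and SAP 6.2: null 0.60, alternative 0.72, SD 0.32, one-sided 0.025, power 80%.

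n = SD² (t_α + t_β)² / (0.72 − 0.60)². With iterated t quantiles this gives 57.8, so 58. The exact noncentral-t calculation also gives 58, with power 0.802. The stated 58 is reproduced. For dropout, 58 / 0.80 = 72.5, against 72 stated. That leaves 72 − 58 = 14 enrolled subjects who may lack a primary value for any reason.

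**2. Time at risk for route (a).** Inputs: a 7-hour FST inside the windows of Protocol Table 2, and wear to 145 h.

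| Group | FST ends (h) | 145 h minus FST end |
|---|---|---|
| Day 1 | 8 to 25 | 120 to 137 |
| Day 3-4 | 56 to 97 | 48 to 89 |
| Day 6 | 128 to 145 | 0 to 17 |

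The target is 145 h or longer, so the upper figures are not strict limits. The hours do not say how many subjects leave, and the documents give no such number.

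**3. What the existing rules give in each case.**

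| Case | Result as written |
|---|---|
| (a) Exit, recorders not downloaded or meter values not entered | Protocol 7.1.3 keeps the data on the recorder until download, and 7.2.4 forms glucose values by merging recorder and meter data. No values, no pairs: outside FAS#2 |
| (a) Exit, downloaded and entered, draw made | Primary value defined |
| (a) Exit, downloaded and entered, no draw made | In FAS#2, primary value not defined |
| (b) Draw made, drawn sensor has no pairs | Primary sensor only, no imputation: no primary value and no substitute |

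Only the third row is open.

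**4. How many subjects could route (b) touch?** Assume that a share f of sensors yields no FST pairs, independently within a subject. The drawn sensor fails while the other works in f(1 − f) of subjects. In 60 subjects:

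- f = 2%: 60 × 0.02 × 0.98 = 1.2
- f = 5%: 60 × 0.05 × 0.95 = 2.9
- f = 10%: 60 × 0.10 × 0.90 = 5.4

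No value of f can be taken from the documents. To count, a sensor must give no pair in a session of about 7 hours sampled about every 15 minutes or more often.

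**5. Cost of omitting such subjects.** Lower limit = 0.72 − t(0.975, n − 1) × 0.32 / √n; power from the noncentral t.

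| Omitted of 60 | n | Lower limit | Power |
|---|---|---|---|
| 0 | 60 | 63.7% | 81.5% |
| 3 | 57 | 63.5% | 79.5% |
| 6 | 54 | 63.3% | 77.2% |

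Subjects who leave early are not completers (SAP 7.1), so route (a) is already in the dropout allowance. Taking it off the 60 completers again would count it twice.

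**6. Other ways of handling them.** If k subjects took the other sensor's value, and this differed by D, the mean would move by kD/60. For assumed D of 0.2 to 0.4, that is 0.003 to 0.007 at k = 1 and 0.02 to 0.04 at k = 6. Scoring them as zero would bring the lower limit to 62.3%, 60.8% and 59.4% for 1, 2 and 3 subjects. The first departs from the primary-sensor restriction and the second is an imputation, so the plan as written allows neither.

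**The case for a change.** The best argument for a change is pre-specification, not power. This is a pivotal study with one test, and the sponsor receives both sensors' data. Step 6 shows that the handling could matter in an extreme case: six substitutions, all 40 points apart in the same direction, would move the mean by 4 points. The margin at the planning values is 63.7 − 60 = 3.7 points. The rules to include withdrawn subjects and to use data up to exit also pull towards giving each of them a value, without saying which sensor supplies it.

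Part of this stands. No section says that the draw is made for a subject who completes the FST and does not reach Visit 5. A sentence saying that download, meter entry and draw are done when the devices come back would do no harm, nor would a listing of FAS#2 members without a primary-sensor pair.

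The rest does not carry. Substitution is not an open option, because both documents tie the endpoint to the primary sensor. Protocol 9.4 orders the draw for each subject, and it is electronic and random. Made at device return or later, it is still independent of the readings, so a late draw introduces no bias. Withdrawn subjects must return their devices (Protocol 9.13) and have an Exit form completed (Protocol 9.2.4.3), the same form that is completed at Visit 5. The natural moment for these tasks therefore exists. If a recorder is never returned, no wording can supply the data.

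**Conclusion.** No change to the plan follows. The definitions of the efficacy set and of the endpoint do not match word for word, but the existing rules settle every case except one: a subject who leaves after the FST, whose recorders are downloaded and meter values entered, and for whom nobody makes the draw. An analyst would either have the draw made or report the subject as having no primary value. Neither choice favours a result.

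The most that the plan as written does is leave a few subjects out of the t-test. At the planning values (72%, SD 0.32), leaving out 3 or 6 of 60 lowers the limit by 0.2 or 0.5 points (63.7% to 63.5% or 63.3%) and power by 2.0 or 4.3 points. The third omission takes power just under 80%, and the conclusion against 60% is unchanged. No direction of bias can be shown.

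This rests on two assumptions: that the number affected is no larger than the 1 to 6 of 60 considered here, a range that the documents neither give nor contradict, and that the primary-sensor restriction and the ban on imputation are applied as written.

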9.5. Assessment of Safety

Adverse Event information is collected in this study. See Section 11 for further information on the collection of Adverse Events and safety information.

9.6. Replacement Sensors

If subjects have either of the sensors which has dislodged any time prior to YSI FST visit or within a duration of 5 hours YSI FST, subject will be asked to re-insert both sensors. And re-insertion of Enlite Sensors will be done only once.

Any YSI FST with a duration of 5 hours or more before sensor dislodgement will be considered complete and will not need to be rescheduled.

Subjects will be issued replacement Enlite sensors to be inserted at Clinic but at the date and time specified by the Clinic.

Subject will wear the replaced sensors for 6 days and attempt to complete the required YSI FST visit.

Subjects will have their YSI FST visit rescheduled per the original randomized FST Group.

9.7. Repeat Rules for In-Clinic Procedures

- Concurrent failure of both the primary and back-up YSI instruments (if applicable) during YSI FST.
- If a sensor dislodges prior to YSI FST, the sensor will be replaced per sponsor's recommendation.
- If subject experiences unresolved IV occlusions during YSI FST requiring fingerstick measurements for a prolonged time period, the FST procedures may be rescheduled per sponsor recommendation.

9.8. Medical Oversight

In order to conduct the YSI FST, staffing with the appropriate training is required:

- A nurse, physician or mid – level provider, such as a nurse practitioner or a physician assistant must be available during the entire YSI FST.
- Deviation from pre-specified protocol requirements for subject safety per investigator discretion is allowed.
- Investigator discretion may be used for management of patients diabetes.

9.9. YSI FST Instructions

9.9.1. Monitoring During the YSI FST

The frequency of blood draws for YSI FST sampling is dependent on the value of the previous sample, according to the following ranges:

- less than ($<$) 75 mg/dL (4.2 mmol/L); every 5 minutes (3-8 minutes)
- greater than (\geq) 75 mg/L (4.2 mmol/L); every 15 minutes (7-23 minutes)

9.9.2. YSI FST Not Available (For Example, IV Occlusion)

In the event that YSI BG values are not immediately available, for safety purposes, the investigational center may use a Study Meter to measure glucose. The fingerstick glucose values will be recorded on the appropriate eCRF and not used for analysis.

CIP313 Clinical Investigation Plan

10688326DOC

Version B

Page 46 of 87

The Medtronic logo consists of a square divided into four quadrants. The top-left and bottom-right quadrants are light blue, while the top-right and bottom-left quadrants are dark blue. The word "Medtronic" is written in white, sans-serif font across the bottom-right quadrant.

Medtronic

Venous blood samples should still be drawn for YSI FST.

9.10. Glucose and Glycemia Measurements

During the course of the study, the subjects' BG, sensor glucose levels, A1C, and alternate POC BG values will be assessed using the following methods:

- **Daily BG-** Values will be assessed during the study by all subjects using the Study Meter. A QC test will be performed on the meter assigned to each subject before being dispensed and before each YSI FST. The results of the QC test will be documented in the subject's source documents. The QC test will be done following the manufacturer's user guide. Subjects will be trained on the use of the Study Meter per the manufacturer's user guide.
- **YSI FST BG values** -During the YSI FSTs at the investigational center, blood plasma glucose will be determined using the laboratory BG analyzer (YSI).
- **Sensor glucose values** - Assessed using the following methods:
 - Sensor glucose values collected by subject's iPro2 and calibrated by subject's Study Meter.
- **A1C** - Collected at baseline and will be used as demographic information.
- **Alternate POC BG values-** During the YSI FST at the investigational center, alternate POC BG measurements will be used (Study Meter) and the values recorded on the appropriate eCRF (not used for analysis). A QC test will be performed on the alternate POC BG device before each YSI FST. The results of the QC test will be documented in the subject's source documents. The QC test will be done following the manufacturer's user guide.

9.11. Recording Data

All data required for analysis will be captured on eCRFs using Oracle Clinical Remote Data Capture's (OC-RDC) module. Original eCRFs will not be used to capture raw/source data and supporting documentation will be required. Patient Log Sheet and subject questionnaires on paper are considered source data, then source data is transferred to an eCRF.

Electronic device data will be collected from the iPro2 using Medtronic CareLink iPro. Certain data points stored in the downloaded information may also be captured on the appropriate eCRF. These data files will be sent to the sponsor electronically using the internet and a secure cloud-based site (Box).

Electronic data files will be collected from the YSI devices for each subject. These data files will be sent to the sponsor electronically using the internet and a secure cloud-based site (Box).

Laboratory results will be recorded on eCRFs.

The investigator will ensure that all eCRFs are completed promptly, completely, and accurately. Information on case report forms must conform to the information in the source documents. Medtronic will provide detailed instructions to assist with eCRF completion. In the event of data discrepancies, investigational centers will be asked to resolve queries electronically in the OC-RDC system; otherwise,

irresolvable data-related issues will be routed to the sponsor for review and final disposition. An audit trail is maintained in OC-RDC to capture any corrections or changes of the eCRFs. If a person is only authorized to complete CRFs or to make changes to an already signed CRF, the investigator shall re-sign this CRF. System backups for data stored in the OC-RDC system will be consistent with Medtronic standard procedures.

Medtronic will only consider eCRFs to be complete when all discrepancies have been resolved, verification has been completed by the monitor and if required, the investigator has approved. It is expected that the investigator and his/her staff will cooperate with the monitoring team and provide any missing data in a timely manner.

